1. PROJECT TITLE

Novel Executive Function Training for Obesity (NEXT)

4. ESTIMATED DURATION OF THE STUDY

5 years

5. LAY LANGUAGE SUMMARY OR SYNOPSIS (no more than one paragraph)

Currently, the best behavioral treatments for obesity only work for 50% of adults, and of those who initially succeed, most do not maintain their weight loss. One reason for this failure may be due to neurocognitive deficits found among individuals with obesity, particularly related to executive function, which make it difficult for these adults to adhere to treatment recommendations. Executive function are mental processes that enable us to plan, focus attention, remember instructions, and juggle multiple tasks successfully. The proposed study aims to develop a Novel Executive Function Treatment (NEXT), which when administered prior to the behavioral treatment, could help improve outcomes by addressing the neurocognitive deficits in adults with overweight or obesity.

6. SPECIFIC AIMS

Aim 1: Develop an initial treatment manual for NEXT.

Aim 2: Iteratively pilot NEXT on two cohorts of participants, and collect qualitative feedback which will be integrated into the NEXT program. (Study 1)

Aim 3: Determine feasibility and acceptability of NEXT (Study 1 & 2)

Exploratory Aim: Evaluate Mediators and Moderators of NEXT (e.g, depression, eating behaviors, self-efficacy)

Aim 4: Establish preliminary effects of NEXT on weight loss, executive function, and self-monitoring through a randomized-control trial comparing NEXT + behavioral weight loss (BWL) to BWL alone (Study 2)

7. BACKGROUND AND SIGNIFICANCE

Nearly two thirds of adults in the United States are overweight or obese. The most successful obesity treatment to date is Behavioral Weight Loss (BWL); however, up to half of adults do not respond to BWL initially, and most responders do not maintain a clinically significant weight loss. The recommendations and

strategies provided by BWL to change behaviors require high levels of executive function (EF), including planning, decision making, and problem solving.⁵ Thus, it is possible that obesity treatment failure is due to impaired neurocognitive mechanisms that negatively impact an individual's ability carry out the recommended behavioral strategies, resulting in non-adherence to treatment or failure to maintain behavioral changes.

Research has shown that individuals with obesity demonstrate difficulties with EF across numerous domains.⁵⁻⁹ Specifically, impairments have been shown on measures of decision making, ¹⁰⁻¹² set-shifting, ^{8,13} planning, ⁹ inhibition, ⁵ working memory, ¹⁴ and fluency ⁵. Better initial performance predicts weight loss and improvement on some of these tasks was seen after weight loss due to bariatric surgery. ^{15,16} A recent NIH Working Group Report ¹⁷ concluded that a need exists for a "deeper understanding of cognitive function" including: 1) the impact on physical activity and eating behaviors, and 2) if it can be used to develop more impactful strategies for weight loss and maintenance. Training EF is consistent with these recommendations and could be a promising mechanism which can be targeted to improve BWL outcomes.

Cognitive training, which targets aspects of EF, has improved cognitive performance and functional outcomes in healthy individuals and various populations with cognitive impairments. ¹⁸⁻²¹ Cognitive training has improved delay discounting among individuals with substance use disorders, ²² and inhibition and attention training paradigms in the context of high calorie foods have been associated with reduced palatable food consumption, reduced binge eating, and increased weight loss. ^{23,24} Cognitive Symptom Management and Rehabilitation Therapy (CogSMART) is a manualized compensatory cognitive training intervention targeting EF which is efficacious among individuals with traumatic brain injury. ^{25,26} A similar intervention is efficacious with individuals with psychosis. ²⁷ Modifying and applying CogSMART to address EF deficits found in people with overweight or obesity could improve weight loss and maintenance outcomes.

Computer training programs targeting implicit neurocognitive processes (i.e., attention, inhibition) show preliminary effects to change eating behavior and weight. ^{23,24} A number of experimental studies have demonstrated training inhibition can impact eating behavior and weight loss. ²⁴ Thus, it is promising that changing elements of EF can improve treatment outcomes.

8. PROGRESS REPORT

Study 1 treatment materials were developed and recruitment of participants began in May 2019. The first group of 10 participants began baseline assessments in June 2019 and started in a 12-week pilot group in July 2019. The group program ended in October 2019 and 8 of 10 participants completed their post-treatment assessments thereafter. Some revisions were made to treatment materials based on feedback received from participants. Recruitment for the second pilot group began in September 2019 and participants completed baseline assessment visits thereafter. The second pilot group began group sessions in November 2019 and finished in February 2020 and 8 of 11 participants completed their post-treatment assessments.

Study 2 recruitment began in February 2020.

[name], the PI, has closely monitored the study. Recruitment has progressed according to plan for Study 1. There have been no formal reports given that no adverse events have occurred and all monitoring has been conducted by the PI and other internal team members.

Study 2 recruitment was recently completed.

9. RESEARCH DESIGN AND METHODS

INTERVENTIONS:

NEXT will be an adjunctive program to the gold standard behavioral treatment for obesity, Behavioral weight loss (BWL). NEXT is based on CogSMART²⁵ and Compensatory Cognitive Training, developed by co-mentor [name], which has been successful at improving EF skills such as planning, problem solving, and cognitive flexibility in individuals with psychiatric disorders or history of traumatic brain injury. I will also use Cognitive Remediation Therapy for AN to inform NEXT.²⁸ NEXT will focus on teaching compensatory strategies, habit learning, and plan for generalization to real-world behaviors (e.g., self-monitoring of food intake). Each session will include interactive exercises to help train an aspect of EF. Skills taught will be

presented to be practiced with real-world applications. For example, planning skills will be taught and participants will apply the skills learned into developing a weekly meal plan, which is a skill suggested in BWL to help with tracking and staying within the recommended calorie range. The EF domains targeted by NEXT were carefully selected to enhance the EF domains (e.g., planning, organization) which underlie the successful use of skills recommended in BWL. BWL recommends skills, but does not provide in-depth, step-by-step training in these basic functions. As part of NEXT, participants will receive compensatory strategies to overcome deficits in underlying EF that could impede success in BWL. Furthermore, NEXT will teach when it is most advantageous to use these skills with particular attention towards training how the skills can be used in the context of aiding weight loss. For example, BWL encourages participants to plan meals ahead of time. NEXT will provide step-by-step strategies to improve meal planning, such as researching recipes, creating efficient shopping lists, organizing shopping in the store, and using similar ingredients in multiple meals. Implementation of meal planning will also be addressed in NEXT, such as when to purchase ingredients and when to prepare meals to be successful. Additionally, participants in NEXT will practice meal planning in session and will complete practice worksheets to improve chances of success in meal planning outside of group. NEXT will provide an additional benefit in that the cognitive skills taught can be used to improve EF across all domains in life, which could potentially decrease stress and improve quality of life.

BWL includes daily self-monitoring of calorie intake and physical activity. Calorie goals will be shaped down to 1200-1400 calories for females and 1500-1700 for males. Physical activity recommendations will be consistent with guidelines suggesting a minimal of 150 minutes of at least moderate intensity activity each week with the ideal being >250 minutes. Lifestyle activity goals focus on building increased activity into typical, daily activities, such as walking or bicycling. Participants are also instructed to decrease sedentary behaviors, such as TV watching or computer usage outside of work. Participants will be encouraged to work toward achieving 10,000 steps per day. BWL will include elements of behavioral change recommendations including stimulus control, self-monitoring, goal setting, managing high-risk situations, meal planning, slowing eating, problem solving, social support, cognitive restructuring, lapse and relapse prevention skills, and maintaining weight loss.

Study 1: This is a study to aid in treatment development of a Novel Executive Function Treatment for Obesity (NEXT) and thus the design will be open label. After consenting to be a part of the study, participants will attend an in person assessment visit which will take approximately 3 hours. Then when enough people have completed assessments and meet inclusion criteria, they will attend a pilot program group (approximately 10-15 other adults). Group will meet weekly for 12 weeks and be scheduled for 75 minutes. There will be another inperson assessment that will take approximately 3 hours following the 12 weeks of pilot program groups.

Group programs will consist of 12 weekly, 75 minutes groups consisting of NEXT only, NEXT and BWL or BWL curriculum only.

Study 2 will consist of a randomized control trial. Study participants will consist of at least 64 adults who will be randomized to one of two conditions, one which will receive NEXT + BWL and one which will receive BWL alone. Each group will consist of 10-20 participants. Study participants will be blind to their condition. All groups will be twenty 75-minute sessions over the course of 6 months. Groups will be held inperson or via password-protected ZOOM meetings. If groups are held via ZOOM, on treatment nights, participants will be sent treatment materials and information on how to access the meetings via email.

Assessment measures are specified below but assessments will occur at two additional time points for a total of four assessments per participant: baseline, at mid-program (take place approximately between sessions 10-14), post program, and 6 month follow-up. Assessment visits will be held in-person or in password-protected ZOOM meetings. Links for assessment tasks that can be completed online including computer tasks and surveys will be emailed to the participant before the assessment appointment with instructions on how to access the ZOOM meeting.

Table 1. Measurement table and assessment time-points for study 2:

	Instrument	Baseline	During group visits	Mid- program	Post- Program	6-month f- up
Anthropometry	Height/Weight	Х	Х	Х	Х	Х
	WRAT-4	Х				
Screening Measures	MINI	Х			Х	x
	Medical and medications	X		Х	Х	Х
Binge Eating	EDE	Х		Х	Х	Х
	EDEQ	Х	Х	Х	Х	X
	DKEFS	X		Х	Х	X
Executive Function	BRIEF	Х			Х	X
	PSI	Х		Х	Х	X
	Delay Discounting	X		X	X	Х
	Brain Health Index	X		Х	Х	X
	DFLEX	Х	X	Х	Х	х
	Digit Span	X		Χ	Х	Х
	WCST	X		Х	Χ	×
	CVLT- Food	X	X	X	Χ	×
	Stop Signal Task	X	X	Χ	X	X
	Tower of London	X	X	Χ	X	Х
	ТМТ	X	X	Х	Х	х
	СРТ	Х		Х	Х	Х
	PHQ-9	Х		X	X	х
	DERS	Х		Х	Х	х
Questionnaires psychiatric	GAD-7	X		Х	Х	х
Questionnaires stress	PSS	Х		Х	Х	×
Questionnaires eating behavior	YFAS 2.0	Х		Х	Х	х
	EAH	X		X	X	X
	Adult Eating Behavior Questionnaire (AEBQ)	Х		Х	Х	Х

	Reward Based Eating Drive Scale (RED)	Х		х	Х	Х
Questionnaires impulsivity	S-UPPS-P	Х	Х	Х	X	X
Questionnaires-self-efficacy	General Self Efficacy Scale	Х	Х	Х	Х	Х
Questionnaires other health behaviors	GPAQ	Х		Х	Х	Х
	Godin leisure time exercise questionnaire	X	X	X	X	X
	Q-LES-Q-SF	Х	Х	Х	Х	X
Adherence	ADH	Х		Х	Х	X
	BWL	X		X	X	×
Feasibility/Acceptability	Attendance		Х	Х	Х	Х
	Acceptability survey		X	X	X	×
Self-Monitoring	Habit books		Х			

Measurements

Screening Measures (baseline only): Participants will complete the Mini-International Neuropsychiatric Interview (MINI)²⁹ to confirm eligibility (i.e., absence of exclusionary psychiatric condition). The WRAT³⁰ reading assessment will be administered at baseline to evaluate reading level and ensure valid administration of the assessments.

Anthropometry (all assessment timepoints and each program visit): At CHEAR Height will be measured using a portable Schorr height board (Schorr Inc, Olney, MD) in triplicate. Height will be recorded to the nearest 0.1 cm. Body weight in kilograms will be measured in triplicate on a Tanita Digital Scale (model WB-110A). Body weight will be recorded to the nearest 0.1 kg. The average of the 3 height and weight values will be used for analysis. Height and weight will be converted to body mass index (BMI=[kg/m²]). If height and/or weight is not collected at CHEAR, participants will be asked to self-report their height and weight using a scale they own or a Bluetooth provided scale.

Binge Eating (all assessment timepoints): The Eating Disorder Examination³¹ (EDE) interview will be administered as the EDE is the gold standard for assessing binge eating is a valid and reliable measure.

Executive Function (all assessment timepoints): Standardized, well-validated neurocognitive tests to assess a broad range of EF domains will be conducted. We will include selected subtests from the widely used Delis-Kaplan Executive Function System (D-KEFS)³² and various other well-validated measures of EF. Lastly, self-report measures of EF are included. Administration of all EF tasks should take about 80 minutes.

BRIEF: To identify individuals with EF difficulties, the Behavior Rating Inventory of Executive Function – Adult³³ (BRIEF-A) will be administered at baseline and again at post-program.

D-KEFS. ³² The D-KEFS is a widely used battery of EF that has strong validity and comparable reliability to other neuropsychological tasks. Three D-KEFS subtests (Color-Word Interference [CWI], Design Fluency, and

Verbal Fluency) will be administered.

Problem Solving Inventory (PSI).³⁴ Participants rate statements describing their own problem-solving behaviors and attitudes using 32, six-point Likert-type items. Three factors are derived: Problem Solving Confidence (self-assurance while engaged in problem solving), Approach-Avoidance Style (tendency to approach or avoid different types of problem-solving activities), and Personal Control (control over emotions and behavior while problem solving). The PSI has strong validity and reliability.³⁵

Delay Discounting³⁵ – Participants choose between two hypothetical rewards, one sooner and one more in the future to measure decision making.

Brain Health Index ³⁶ – the Brain Health Index includes a measure of nonverbal reasoning and processing speed which provide an index of general cognitive functioning and allow interpretation of other executive function tasks. These tasks are briefly administered on the computer.

Digit Span³⁷ -- The Wechsler Digit Span Task is a well-established measure of short-term memory. The test administrator reads 1 digit per second. The participant must repeat the digits verbatim. The number of digits increases by one until the participant consecutively fails two trials of the same digit span length.

Wisconsin Card Sort Test (WCST)³⁸- The Wisconsin Card Sort Test is a well-validated neuropsychological measure of "set-shifting", or how well a participant can adapt to changing rules. The participant is presented with a number of stimulus cards that can be matched in three ways: the color of its symbols, the shape of its symbols, or or the number of shapes on each card. The participant must classify cards without knowing the classification rule and only receiving feedback on if the classification is correct or not. The classification rule changes every 10 cards.

California Verbal Learning Test (CVLT) – Food³⁹ -- The California Verbal Learning Test-II consists of two lists that are read aloud. Each list is comprised of 16 words drawn from 4 semantic categories (e.g. furniture), with 4 words per category. The first list (list A) is read 5 times followed each time by an immediate free recall test. The second list (list B) is then read, also followed by an immediate recall test. Then short-delay free- and cued-recall of list A is measured followed by a 20-minute non-verbal distractor task (Stop Signal Task- see below). Finally, long-delay free- and cued-recall and recognition of list A are tested. The CVLT-II generates over 30 indices that help to understand an individual's learning strategies. The CVLT-food is identical except for one category of words (4 words) is replaced with high calorie food words that are matched on word frequency with those of the original CVLT-II.

Stop Signal Task-Food Version⁴⁰- The Stop Signal Task measures inhibition to food and non-food cues. On each trial, participants are asked to discriminate between a picture of calorically-dense food or neutral object (e.g, chair). The two primary outcomes, stop signal reaction time for food pictures (SSRT-food) and neutral pictures (SSRT-neutral) will be compared to assess for food-specific impulsivity versus general impulsivity.

Tower of London⁴¹ – The Tower of London test is an extensively used measure of mental planning. Participants move disks between pegs of different lengths one at a time to match a sequence that has been presented to them in the fewest number of moves possible.

Trail Making Test (TMT)⁴²- The Trail Making Test is an extensively used neuropsychological test of visual attention and task switching. Participants are instructed to connect a sequence of 25 dots as quickly as possible first connecting numbers, then letters, then switching between numbers and letters.

Continuous Performance Task (CPT)⁴³ – The Continuous Performance Task is a neuropsychological test that measures a subject's sustained and selective attention. Participants must press a key when a certain stimulus is presented but ignore other stimuli.

Questionnaires (all timepoints): Standardized questionnaires will also be assessed to evaluate psychiatric symptoms, stress, eating behavior, impulsivity and self-efficacy. The following questionnaires will be

administered: Eating Disorder Examination Questionnaire (EDEQ)⁴⁴, Detail and Flexibility Questionnaire (DFLEX)⁴⁵, Short-form of the UPPS-P Impulsive Behavior Scale (S-UPPS-P)⁴⁶, Perceived Stress Scale (PSS)⁴⁷, Yale Food Addiction Scale 2.0 (YFAS 2.0)⁴⁸, Patient Health Questionnaire – 9 (PHQ9)⁴⁹, Quality of Life Enjoyment and Satisfaction Questionnaire – Short Form (Q-LES-Q-SF)⁵⁰, General Self Efficacy scale⁵¹, Adult Eating Behaviour Questionnaire⁵², Eating in the Absence of Hunger⁵³, Reward Based Eating Drive Scale⁵⁴, global Physical Activity Questionnaire⁵⁵, godin leisure time exercise questionnaire⁵⁶, GAD 7⁵⁷, Difficulties in Emotion Regulation Scale (DERS)⁵⁸

Adherence: Frequency of behaviors and skills taught in the program (e.g., self-monitoring, use of calendar, problem solving, exercising) will be assessed to evaluate whether treatment impacts behavior.

Feasibility and Acceptability (post-program only). Feasibility will be assessed by attendance of participants in program sessions. Acceptability will be assessed by survey (all time points except baseline), created by the study team based on established surveys used for [name] current studies (e.g, IRB 151110). Likert-type ratings will be used to respond to questions, such as "How much did you enjoy the program?" and "How helpful did you find the program?" Participants will also be asked to complete a brief interview to describe their experience and respond to certain aspects of program to provide qualitative data to be used in future program development.

Self-Monitoring (at each program visit). At each program session, participants will turn in self-monitoring from the previous week and ratings of adherence will be assigned daily based on completeness of entry.

Audiorecording: All program sessions and assessments will be audiotaped for the purposes of supervision and fidelity. As audiotaping is required, participants will not need to sign a supplemental consent as this will be specified in the standard consent form.

Data collection protocol. The data for this study will include a number of different methods of collecting data. The questionnaires will be available as a secure web-based survey. All surveys and computer tasks administered online will be identified with the unique study ID rather than any identifying information. All interview data and executive function tasks will be collected under the unique ID. Following the first assessment visit, participants will be given the option of completing some surveys via the secure-web-based survey format prior to attending the in-person visit to reduce the amount of time they need to be present at CHEAR. If participants do not complete the surveys in advance, they will complete them as part of the visit. For survey questions completed at home that may warrant immediate follow-up (i.e., questions about suicidal ideation or self-harm), a REDCap alert via email will be set up to notify the study coordinator when those questions are complete. The study coordinator will check these alerts every business day and will send appropriate resources if the participant endorses suicidal ideation or self-harm. All assessors will be trained and certified in the tasks and interviews and supervised by the study PI. De-identified data will be stored in a database. It may be shared with others to aid future research efforts or put in a repository as recommended by the NIH. No identifying information will be kept with the data for future efforts or if entered into a repository. Permission to use this de-identified data has been included in the consent form for future studies on obesity, weight loss or executive function. It specifies that all identifiable data will be removed. The dates that data were collected will not be shared – only the length of time between collections will be provided to aid anonymity. The de-identified data will be kept by [name] according to procedures identified with data storage below and she will only share data with those who have received permission to use it (e.g., have an approved exempt protocol).

Data Analysis and Interpretation: The pilot aspect of this study is to help evaluate the feasibility and acceptability of the program to aid in program development for a future randomized control trial. Data analyses will consist primarily of descriptive data, evaluating weight loss change and changes in executive function by evaluating pre and post assessment changes. Qualitative data will be used to continue to improve the NEXT

program development. Women and minorities will be included in recruitment for this study. Typically previous weight loss studies have had \sim 75% women participants.

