10. HUMAN SUBJECTS

Study 1: It is expected that up to 60 individuals may be consented with a goal to have at least 20 participants enroll in pilot program who meet the following eligibility criteria for study 1, Inclusion criteria:

- 1. Age 18-65
- 2. Ability to read English at a 6th grade level
- 3. BMI >25 and <45
- 4. Difficulties with executive functioning

Exclusion Criteria:

- 1) Medical condition that requires physician monitoring to participate in weight control program or prohibits safely participating in recommended physical activity
- 2) Psychiatric condition that could interfere with program participant (e.g., substance abuse, suicide attempt within previous 6 months, active purging)
- 3) Currently pregnant, lactating or plan to be in the timespan of program follow-up
- 4) Current enrollment in an organized weight control program
- 5) Change in psychotropic medication or other medication that could have impact on weight during the previous 3 months
- 6) History of bariatric surgery
- 7) History of learning disorder, neurological condition or injury

Study 2: It is expected that up to 150 participants may be consented with the goal to have at least 64 participants randomized to start group in study 2 with the same eligibility criteria that was used in Study 1 (presented above).

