15. RISK MANAGEMENT PROCEDURES AND ADEQUACY OF RESOURCES

Risks of psychological assessments: Participants will receive consistent support from the study staff throughout the study. Participants will be told that they are free to choose not to answer any questions that may cause them distress if they wish.

For any unidentified/unreported psychiatric concerns identified during assessments for this project, we will execute the following protocol:

- 1. Participant will be notified of concerns identified.
- 2. Participant will be given a list of referrals in the community.
- 3. If significant concern is warranted (participant reports suicidal ideation, significant binging and purging), participants will be immediately assessed by the clinical staff or a licensed clinical psychologist present at the meeting regarding severity and an appropriate psychiatric referral will be made. If the assessment visit is held via ZOOM, a clinical staff member or licensed clinical psychologist will join the ZOOM meeting to assess the participant for severity. Participants experiencing significant psychological distress or discomfort will be discontinued from the protocol and referred for counseling with their consent. If suicidal ideation is reported, thorough suicide risk evaluation consisting of the assessment of past suicide attempts, plans,

availability of means, and current stressors to evaluate extent of risk will be conducted. A safety plan will be completed in collaboration with the participant and referrals will be made for therapy or to a crisis center. If the participant appears to be at imminent risk for suicide, the clinician will call 911.

Potential risk of program: Participants will receive consistent report from study staff. If significant distress occurs during program, they will be allowed to take a break from program and talk to one of the study staff. If suicidal ideation is reported the above protocol will be followed.

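### Suicidal ideation reported in a home survey has a weaker stated response than at a visit, and significant binging and purging, if asked about at home, has no stated alert

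*Combined protocol and SAP*

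**What the plan says.** Section 9, Data collection protocol, puts the questionnaires online: "The questionnaires will be available as a secure web-based survey". After the first assessment visit, participants may complete some surveys, which are not named, before they attend. For Study 2, Section 9 adds: "Links for assessment tasks that can be completed online including computer tasks and surveys will be emailed to the participant before the assessment appointment".

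The same paragraph provides one safeguard for answers given at home, an emailed alert to the coordinator. Its scope is "For survey questions completed at home that may warrant immediate follow-up (i.e., questions about suicidal ideation or self-harm"), and the action is: "The study coordinator will check these alerts every business day and will send appropriate resources if the participant endorses suicidal ideation or self-harm".

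Section 15, under risks of psychological assessments, deals with psychiatric concerns that come to light during assessments. The participant is told of the concern and given referrals. Then: "If significant concern is warranted (participant reports suicidal ideation, significant binging and purging), participants will be immediately assessed by the clinical staff" or by a licensed psychologist at the meeting. If the visit is on ZOOM, a clinician joins the call. Reported suicidal ideation also brings a thorough risk evaluation and a safety plan, and an emergency call if risk is imminent.

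Table 1 schedules the EDE interview at all four Study 2 assessments, and marks the MINI at baseline, post-program and 6-month follow-up. Section 10 excludes, at entry, "Psychiatric condition that could interfere with program participant (e.g., substance abuse, suicide attempt within previous 6 months, active purging"). Binge eating is not a named exclusion.

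**The concern.** The investigators saw that a worrying answer given at home needs its own route to staff, and they built one. It falls short of the plan's own standard in two ways.

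First, suicidal ideation disclosed at a visit leads to a clinician and a structured risk evaluation. Disclosed in a home survey, it leads to a business-day check by the coordinator and the sending of resources. A coordinator who follows Section 9 to the letter has done what it asks without any clinician speaking to the participant.

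Second, Section 15 names significant binging and purging next to suicidal ideation as grounds for immediate assessment. The home alert leaves it out, and the wording is closed (i.e., not e.g.).

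What is at stake is a late or weaker clinical response for an individual participant. No trial result depends on it.

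**Working it through.** No arithmetic settles this point; the check sets the two sections side by side.

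| | Reported at a visit (Section 15) | Reported in a home survey (Section 9) |
|---|---|---|
| Suicidal ideation: who acts | Clinical staff or licensed psychologist | Study coordinator |
| Suicidal ideation: when | Immediately | At the business-day check |
| Suicidal ideation: action | Risk evaluation, safety plan, referral; emergency call if risk is imminent | Resources sent |
| Significant binging and purging | Immediate clinical assessment, referral | No alert, reader or review time stated |

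**Step 1. Can answers be given at home?** Yes. The option opens after the first assessment visit. Study 2 has four assessments, so it applies at 4 − 1 = 3 of them. The emailed links could add baseline, since that sentence makes no exception for it.

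**Step 2. Suicidal ideation and self-harm.** The alert covers both. The shortfall lies in the response: a different person, a later time and a lesser action. An answer submitted after Friday's check waits until the next business day.

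**Step 3. Significant binging and purging.** The alert does not cover it. Whether this matters depends on which surveys are done at home. Section 9 lists the EDE-Q among the questionnaires, and Table 1 places it under binge eating. The plan does not say that it is completed at home, and it does not list its items. This half of the point is therefore conditional.

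**Step 4. What would catch it otherwise?** The EDE interview is scheduled at 4 of 4 assessments. The MINI is marked at 3 of 4 in Table 1 (not mid-program), although the Measurements text describes it as a baseline screening measure. For a participant who attends, the result is a delay until the interview. Its length cannot be computed, because the plan does not say how far ahead the links go out. For a participant who submits the survey and then misses the visit, the plan names no one to read those answers and no time for doing so.

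**Step 5. Does anything else cover home answers?** The Data Safety Monitoring Plan in Section 15 asks participants to report injuries and health problems to the principal investigator. It adds no review of survey responses.

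**Step 6. Statistical consequences.** None. No endpoint, analysis, error rate or sample size depends on the alert.

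**The case against.** The strongest reply is that Section 15 already applies. It speaks of concerns identified during assessments for the project, and Section 9 counts online surveys among the assessment tasks. The notification and referral steps are not tied to a meeting, and the sentence requiring a suicide risk evaluation is not limited to in-person reports. This is a fair reading, and it rules out two stronger ones. A reader might infer that Sections 9 and 15 contradict each other, or that a participant reporting suicidal ideation from home would get no clinical evaluation. The documents support neither. What stands is narrower: where Section 9 deals specifically with home answers, it prescribes the lesser action, and Section 15's immediate step relies on staff at, or joining, a meeting.

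A reader might also infer that purging reported on a home EDE-Q is bound to go unseen. The documents do not establish that the EDE-Q is done at home or what it asks. Active purging is excluded at entry, and the EDE and MINI interviews stand behind the questionnaire. Twenty group sessions give further contact, though no step there reviews survey answers.

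Finally, a reader might try to count those affected from Study 1, where "8 of 10 participants completed their post-treatment assessments thereafter" in the first group and "8 of 11 participants completed their post-treatment assessments" in the second, leaving 2 and 3 without one. That does not carry over. Nothing shows that any of these five had submitted a survey first. Study 2 differs in length, payments and possible ZOOM visits, its target of 64 is a minimum, and the documents give no rate of new binging or purging. No number can be defended.

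**Conclusion.** The point holds as a minor participant-safety gap. For suicidal ideation it rests directly on the text: the written response to a home report is weaker than the response to the same report at a visit. For significant binging and purging it holds only on the assumption that a home survey contains such items. In that case the first stated review is the next EDE or MINI interview.

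The size is small. Participants who attend face a delay rather than a missed concern. The entry exclusion leaves mainly new-onset purging, and binge eating is a measured domain in this trial, so much of it would already be known from baseline. The number affected cannot be estimated from the documents and could be zero.

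**What to change.** Amend the Data collection protocol paragraph of Section 9 in two places.

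1. For each home alert on suicidal ideation or self-harm, have the coordinator pass it to clinical staff, who contact the participant and carry out the Section 15 risk evaluation. Sending resources then becomes an addition to that contact.
2. Where a home survey contains such items, add Section 15's own trigger to the same REDCap alert: newly reported significant binging and purging, at a threshold the investigators set in advance, with the same clinical follow-up. An alert on any purging at all would go beyond the plan's standard and is not needed.

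It would help to name the surveys offered for home completion, so that staff know whether the second change applies.

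The cost is a short protocol edit, one more alert rule, an agreed threshold, and clinical staff time for each alert. No new staff are needed. Some extra alerts will follow, and the threshold and the restriction to new reports keep them down. Section 8 says Study 2 recruitment is complete, so the change helps only at assessments still to come.
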